# 10.5 Events Requiring Immediate Reporting

#### 10.5.1 Serious Adverse Events

SAEs must be reported from the investigational site to the sponsor no later than 24 hours following:

- The subject's visit at which such AE was reported, noted, or recognized;
- The principal investigator's or any investigator personnel's receipt of the test results; or
- Other information from which such development was reported, noted, or recognized.

#### 10.5.2 Overdose/Medication Errors

An overdose is defined as a subject receiving a dose of GEN1044 in excess of 10% of that specified in this protocol. All cases of overdose must be reported to the sponsor as protocol deviations within 24 hours of knowledge of the event (see additional details in Section 10.5.2.1).

Medication errors (including infusion rate errors) and uses outside what is foreseen in the protocol, including misuse and abuse of the product, should be reported within 24 hours of knowledge of the event.

# 10.5.2.1 Treatment of Overdose

Rescue medication to reverse the action of GEN1044 is not available. In case of overdose, medication errors, misuse and/or abuse of the trial drug, subjects should receive supportive care according to local guidelines and potential side effects of GEN1044 should be treated symptomatically.

In the event of an overdose, the investigator should:

• Contact the sponsor's medical monitor immediately.

Version: 4.0

- Closely monitor the subject for any AE/SAE and laboratory abnormalities
- Consider plasmapheresis, in consultation with the sponsor.
- Obtain a serum sample for PK analysis if requested by the sponsor's medical monitor (determined on a case-by-case basis).
- Document the quantity of the excess dose as well as the duration of the overdose.

# 10.5.3 Pregnancy

Pregnancy is not allowed in this trial. However, if any pregnancy occurs during trial participation, the pregnancy must be reported.

All reports of pregnancy in female subjects or partners of male subjects must be reported to the sponsor within 24 hours of knowledge of the event. In the case of pregnancy in the partner of a male subject, a separate ICF will be obtained from the female partner for collection of information regarding the pregnancy.

The pregnancy must be followed-up to determine outcome (including premature termination) and status of mother and child. The child must be followed at least to the age of 1 month. Pregnancy complications and elective terminations must be reported as an AE or SAE. Spontaneous abortions must be reported as an SAE. Any SAE occurring in association with a pregnancy brought to the investigator's attention after the subject has completed the trial and considered by the investigator as possibly related to the GEN1044 must be promptly reported to sponsor or designee.

Pregnant trial subjects must be withdrawn from treatment immediately, whereas male subjects may continue in the trial should pregnancy of female partners occur.

# 10.6 Regulatory Reporting Requirements for Suspected Unexpected Serious Adverse Reactions

The sponsor has a legal responsibility to notify, as appropriate and according to local regulations, both the local regulatory authority and other regulatory agencies about the safety of the product under clinical investigation. Prompt notification of SAEs by the investigator to the sponsor is essential so that legal obligations and ethical responsibilities towards the safety of subjects are met (see Section 10.5.1).

The sponsor will ensure that all relevant information about Suspected Unexpected Serious Adverse Reactions (SUSARs) is documented and reported as soon as possible, but within a maximum of 15 days (fatal or life-threatening SUSARs within a maximum of 7 days) of first knowledge by the sponsor or designee, to the competent regulatory authorities and/or to the ethics committee/IRBs according to the applicable local regulatory requirements. Relevant follow—up information of fatal or life-threatening SUSARs will be communicated subsequently within the required reporting timelines. The sponsor will also communicate relevant information on SUSARs with the investigators in predefined periods according to local regulations.

The investigator should be aware of local reporting regulations to the IEC/IRB. The safety CRO will either supply the investigator with the reports which should be passed on to the IEC/IRB or report directly to the IEC/IRB, depending on local regulations.

The sponsor will notify all investigators of the SUSAR.

Version: 4.0

# 10.7 Follow-Up of Adverse Events and Serious Adverse Events

All AEs must be followed until they are resolved, or until the safety follow-up visit(s), or the start of new anti-cancer treatment, whichever comes first.

All SAEs and GEN1044-related AESIs qualifying for immediate reporting that are ongoing at the safety follow-up visit should continue to be followed on a regular basis until the event has been resolved or until the investigator assesses it as chronic and all queries have been resolved.

Only SAEs judged by the investigator as related to trial drug should be reported after the safety follow-up period.

# 10.8 Warnings and Precautions

No evidence available at the time of the approval of this trial protocol indicated that special warnings or precautions were appropriate, other than those noted in the provided Investigator's Brochure. Additional safety information collected between Investigator's Brochure updates will be communicated in the form of investigator notifications. This information will be included in the subject informed consent and should be discussed with the subject during the trial as needed.

Version: 4.0

# **10.9 Data Monitoring Committee**

A DMC will be established to ensure the continuing safety of the subjects enrolled in this trial. This committee will consist of at least 1 medical expert in the relevant therapeutic area; committee membership responsibilities, qualifications, and procedures will be documented in its charter.

#### 10.10 Dose Escalation Committee and Safety Committee

The DEC will be chaired by the sponsor's Responsible Medical Officer (or delegate) and membership will include investigator(s), a sponsor clinical scientist, a safety physician, a statistician, a clinical pharmacologist, and other sponsor staff, as appropriate. The DEC will meet at regular frequency throughout the Dose Escalation part.

All available data, including but not limited to safety, pharmacokinetic, and pharmacodynamic data, covering the DLT evaluation period will be reviewed by the DEC. Cumulative data from subsequent treatment doses may also be monitored. Recommendations on dose escalation (or deescalation) will be made by the DEC to the Safety Committee.

The Safety Committee will consider the recommendation made by the DEC and make the final decision regarding dose escalation (or de-escalation). The Safety Committee can also stop further enrollment if treatment-emergent toxicity is determined to result in an unfavorable change in subject benefit/risk. Enrollment may be temporarily held, if needed, for the Safety Committee to evaluate the emerging data.

Decisions will be communicated to investigators and decisions with the potential to affect subject safety (eg, unfavorable change in benefit/risk assessment) will be promptly communicated to investigators and regulatory authorities, as required.

Version: 4.0

#### 11 STATISTICS

The Statistical Analysis Plan (SAP) will be developed and finalized before database lock and will describe the subject populations to be included in the analyses, and procedures for accounting for missing, unused, and spurious data. This section is a summary of the planned statistical analyses of the primary and secondary endpoints.

All presentations will be done separately for the Dose Escalation part and the Expansion part. Subjects in the Dose Escalation part will typically be analyzed according to the assigned DL cohort. Subjects in the Expansion part will be analyzed according to their assigned expansion cohort.

The primary analyses will be timed as follows:

- **Escalation**: Primary safety and efficacy analyses will be conducted on all subject data at the end of the escalation.
- Expansion: The expansion part consists of parallel cohorts, wherein each expansion cohort may report its individual primary analysis. Primary safety and efficacy analyses will be conducted on all subject data at earliest when all subjects who are still receiving trial treatment have at least 2 scans performed (such that the primary endpoint may be confirmed).

#### 11.1 Analysis Sets

The analysis sets are defined similarly for both escalation and expansion parts.

# 11.1.1 Full Analysis Set

The full analysis set (FAS) and safety set are defined in the same way and will comprise all subjects who receive at least 1 dose of trial drug.

# 11.1.2 Response Evaluable Set

The response evaluable set consists of all subjects who have baseline evaluable disease and at least 1 post-baseline disease assessment. It also includes subjects who die before the first response assessment; these subjects are treated as non-responders.

#### 11.1.3 Safety Set

See the definition of the FAS.

#### 11.1.4 Per-Protocol Set

Not applicable.

# 11.1.5 Pharmacokinetic Analysis Set

The pharmacokinetic analysis set (PAS) will include all subjects who receive at least 1 dose of trial drug and who provide at least 1 evaluable PK sample.

# 11.1.6 Immunogenicity Analysis Set

The immunogenicity analysis set (IAS) will include all subjects who receive at least 1 dose of trial drug, and have a baseline and at least 1 evaluable on-treatment ADA sample.

Version: 4.0

#### 11.1.7 Dose-Determining Analysis Set – Dose Escalation Part

The dose-determining set (DDS), which is used to define the number of DLT evaluable subjects on a DL cohort, will include all FAS subjects in the escalation part who meet the exposure criterion (defined below) and have sufficient safety evaluations, or experience a DLT prior to the 2nd full dose administration. The DLT period will extend until 7 days after the first full dose (see Section 4.2).

A subject meets the exposure criterion if all doses, up to and including the 1st full dose, are administered in a timely fashion: In general, the individual doses should not be delayed more than 7 days. However, longer dose delays might be acceptable if the DEC considers the assessments still to be appropriate. The first full dose should be administered at latest by 30 calendar days after C1D1 (if one intermediate dose is administered), or by 38 calendar days after C1D1 (if two intermediate doses are administered), counting the day of first exposure as C1D1.

If there is a longer dose delay the subject is considered as non-DLT evaluable (as long as the reason for the dose delay, or the dose delay itself, is not classified as a DLT). DLTs occurring beyond the DLT period will be presented, but not contribute to the DLT rates for the DL cohort per mBOIN.

Subjects who do not experience a DLT will be considered to have sufficient safety evaluations if they have been observed for  $\ge 21$  days (or  $\ge 28$  days if 2 intermediate doses are applied) following the priming dose, and are considered by both the sponsor and investigators to have enough safety data to conclude that a DLT did not occur.

For a period-specific dose level (doses up to and including 1st full dose), a subject is considered as DLT evaluable if the dose was timely administered (ie, not delayed for more than 7 days) and had sufficient safety evaluations up to the subsequent dose administration to conclude if a DLT did occur or not. The relative DLT periods for priming and intermediate doses extend the planned timing of the subsequent dosing (ie, extends until 7 days after the dose administration). For the 1st full dose, it extends up to 7 days past drug administration. Appendix 9 provides a comparison of the DDS considerations and a template for the reporting of DLT rates.

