## **Appendix 8 Recommended ICANS Management**

Source: (Garcia Borrega et al., 2019; Lee et al., 2019)

<sup>2 Borrega Garcia et al., 2019.

Version: 4.0

## Appendix 9 Description of DLT Rates After Protocol Amendment 3

Table 28 Dose-Determining Analysis Sets Comparison

DLT Consideration	Number FAS	Number DLT Evaluable	DLT Period	Comment
DL cohort	All those with at least 1 dose (ie, prime dose) administered	All those who meet the exposure criteria for the DL cohort, or experience a DLT during the DLT period	Up to 7 days past 1 st full dose administration	Regardless of what individual dose that the DLT could be associated with, the DLT is attributed to DL cohort as such
Period-specific DLT rates	All those administered the period-specific dose	All those administered the period-specific dose in a timely fashion	Up to 7 days past dose administration	

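### Section 11.1.7 is inconsistent on whether a DLT after a dose delayed more than 7 days counts, and the supplementary period-specific rates leave it out

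*Protocol*

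**What the plan says.** **DL-cohort rate.** Protocol Section 11.1.7 opens by defining the dose-determining set through two alternative routes. It takes escalation subjects "who meet the exposure criterion (defined below) and have sufficient safety evaluations, or experience a DLT prior to the" second full dose. The second route carries no timeliness condition. Table 28 (Appendix 9) has the same either/or structure in its DL-cohort row, as does Section 4.2.2. SAP Section 4 also has it, with a fixed 21-day window.

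The second paragraph of 11.1.7 sets the exposure criterion. Individual doses should in general not be more than 7 days late, the DEC may accept longer delays, and the first full dose has an outer limit of 30 or 38 calendar days. The third paragraph then states: "If there is a longer dose delay the subject is considered as non-DLT evaluable". Its only exception is where the reason for the delay, "or the dose delay itself, is not classified as a DLT".

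**Period-specific rates.** For these, "a subject is considered as DLT evaluable if the dose was timely administered (ie, not delayed for more than 7 days") and safety follow-up up to the next dose was sufficient. The matching row of Table 28 counts as evaluable "All those administered the period-specific dose in a timely fashion". Neither place has a DLT route, and the DEC's discretion over longer delays is not repeated there.

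**Use.** Section 4.2.1 says the period-specific rates may be given to the DEC as a supplement to the DL-cohort rate when it considers the next dosing sequence, and that they may be read in the context of Table 11.

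**The concern.** In a first-in-human escalation, whether an observed DLT counts should not depend on which sentence is followed. Delays beyond 7 days are foreseeable, since Section 7.2.1 lets a dose be postponed for up to 6 weeks for an adverse event. If a delayed subject then has a DLT, the third paragraph and the first sentence of 11.1.7 classify that subject differently.

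In the period-specific rows the written rule removes the subject from both numerator and denominator. Removing a subject who had a DLT cannot raise a rate and lowers it unless every subject had one. The DEC could then see a Table 29 in which a DLT appears in the cohort row and in no dose row, while the dose row, read against Table 11, looks cleaner than the experience at that dose.

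**Working it through.** **1. Reproduce the plan's thresholds.** Inputs from Section 4.2.1: φ = 0.30, φ₁ = 0.6 × 0.30 = 0.18, φ₂ = 1.4 × 0.30 = 0.42.

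- λ₁ = ln[(1−φ₁)/(1−φ)] / ln[φ(1−φ₁)/(φ₁(1−φ))] = ln(0.82/0.70) / ln(0.246/0.126) = 0.2365, stated as 24%.
- λ₂ = ln[(1−φ)/(1−φ₂)] / ln[φ₂(1−φ)/(φ(1−φ₂))] = ln(0.70/0.58) / ln(0.294/0.174) = 0.3585, stated as 36%.

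These thresholds, with the termination rule x/(n+3) ≥ λ₂, reproduce every cell of Table 11 for n = 3 to 9.

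**2. Effect of dropping one subject with a DLT.** The rate moves from x/n to (x−1)/(n−1). The fall is x/n − (x−1)/(n−1) = (n−x)/[n(n−1)], which is never negative.

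| Subject counted | Table 11 | Subject dropped | Table 11 |
|---|---|---|---|
| 1/4 = 25% | remain | 0/3 = 0% | escalate |
| 2/7 = 29% | remain | 1/6 = 17% | escalate |
| 2/8 = 25% | remain | 1/7 = 14% | escalate |
| 3/9 = 33% | remain | 2/8 = 25% | remain |

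The first row is four subjects given a dose: three on time without a DLT, and one 9 days late with a DLT within 7 days of it. The last row shows that the recommendation does not always change.

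**3. Which rate does this reach?** Apply each definition to that late subject, assuming the DEC has not accepted the delay and the delay is not itself DLT-related.

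| Definition | Late subject with DLT |
|---|---|
| 11.1.7, first sentence | counted |
| Table 28, DL-cohort row | counted |
| Section 4.2.2, item 3 | counted |
| 11.1.7, third paragraph, read literally | not counted |
| 11.1.7, period-specific paragraph | not counted |
| Table 28, period-specific row | not counted |

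**4. Can the third paragraph be confined to DLT-free subjects?** That is the reading that fits the other places, but the wording does not secure it. If the paragraph covered only DLT-free subjects, its exception would be largely redundant, because a DLT that caused the delay already enters through the first sentence. The next paragraph is expressly limited to subjects without a DLT; this one is not.

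**5. Does the SAP settle it?** No. SAP Section 4 keeps the DLT route and has no 7-day rule, but it fixes the window at 21 days. A full dose due on Day 15 and given 9 days late falls on Day 24. A DLT after it is outside the SAP window but inside the protocol's window of 7 days after the first full dose.

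**The case against.** A reader might infer that 11.1.7 removes these DLTs from the DL-cohort rate, so that an mBOIN remain becomes an escalate. The documents do not support that. The first sentence of 11.1.7, the DL-cohort row of Table 28 and Section 4.2.2 all admit a subject with a DLT whatever the delay. The third paragraph follows the exposure criterion and is most naturally read as the consequence of failing it. The next sentence withholds from the DL-cohort rate only DLTs beyond the DLT period, and those are still presented. The 7-day limit is also soft for the cohort rate, because the DEC may accept longer delays and Section 7.1 lets the DLT period be adjusted for delay. Read this way, 1/4 stays 1/4 and 2/7 stays 2/7. All of this stands, and it leaves only a wording conflict for the DL-cohort rate.

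A reader might also infer that delays usually reflect poor tolerance of the previous dose. The documents give no figure for this: Section 7.2.1 allows postponement for adverse events whether drug-related or not.

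On the period-specific rates, two arguments have weight. They are optional and supplementary; the DEC weighs all data and the Safety Committee decides. Limiting the rows to on-time doses is also a defensible way to describe toxicity at the planned step-up interval. These points lower the severity. They do not explain why a DLT should be absent from the row without any note.

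**Conclusion.** The point holds in two parts.

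- **DL-cohort rate:** a conflict of wording. Three places in the protocol count the DLT and one paragraph, taken literally, does not. The Table 11 changes reach this rate only if that paragraph is allowed to override the other three.
- **Period-specific rates:** a real gap. As written, a DLT after a dose more than 7 days late is left out, and the row can move from remain to escalate, as with 1/4 to 0/3 or 2/7 to 1/6.

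The severity is minor to moderate. The examples assume small rows with a single such subject. The documents do not say how often this occurs, so no overall bias can be quantified. SAP Section 1.2 records that enrolment has stopped, so what remains is mainly how DLT rates are documented and interpreted.

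**What to change.** 1. In the third paragraph of 11.1.7, make a subject with a longer delay non-evaluable only if, in addition to the present condition, *no DLT occurred in the DLT period*. This aligns it with the first sentence, Table 28 and Section 4.2.2.
2. In the period-specific definition in 11.1.7 and the period-specific row of Table 28, add *or who experience a DLT within 7 days of that dose*. If the sponsor prefers to keep those rows to on-time doses, footnote each omitted DLT in Table 29 instead.

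The cost is two clauses, or one clause and a footnote. The statistical price of the second clause is a slightly conservative period-specific rate, because delayed subjects would enter it only when they have a DLT. The footnote avoids that price but leaves the reader to adjust the rate.

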#### 11.2 Subject Disposition

Subject dispositions will be presented in flow diagrams in accordance with the current CONSORT statement.

#### 11.3 Subject Demographics and Baseline Characteristics

Demographic and other baseline data including disease characteristics will be listed and summarized descriptively for the FAS.

Categorical data will be presented as frequencies and percentages. For continuous data, mean, standard deviation, median, minimum, and maximum will be presented.

Relevant medical histories and current medical history at baseline will be summarized by system organ class and preferred term, by cohort or expansion cohort, depending on part.

#### 11.4 Treatments

The FAS will be used for the analyses below. Categorical data will be summarized as frequencies and percentages. For continuous data, mean, standard deviation, median, 25th and 75th percentiles, minimum, and maximum will be presented.

Version: 4.0

The duration of exposure to GEN1044, the cumulative dose administered, and dose intensity (computed as the ratio of actual cumulative dose received and number of cycles initiated) will be summarized by means of descriptive statistics.

The number of subjects with dose adjustments and the reasons will be summarized, and all dosing data will be listed.

Concomitant medications and significant non-drug therapies prior to and after the start of the trial treatment will be listed and summarized according to the anatomical therapeutic chemical (ATC) classification system.

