#### 4.2.1.1 Modifications to BOIN

The BOIN has the following general stopping rules:

- i. Escalation stops if 80 subjects have already been dosed.
- ii. Escalation stops if there are 9 subjects already treated on a DL cohort proposed by the DEC.

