# **6.3** Dosages and Administration

Trial treatment should be administered as described in Section 4.2 (Dose Escalation) and Section 4.3 (Expansion) until one or more of the discontinuation criteria in Section 8.1 are met:

- Cycles 1 through 4: Days 1, 8, and 15 (once weekly for a 21-day cycle)
- Cycles 5 and beyond: Day 1 (every 3 weeks for a 21-day cycle)

Refer to the preparation and administration guideline for additional information and stepwise guidance on dosage and administration.

Detailed dose modification guidance is provided in Section 7. Refer to Section 6.5 for information regarding concomitant therapy.

GEN1044 will be administered using IV infusion on Days 1, 8, and 15 of each 3-week (21-day) treatment cycle. GEN1044 will be administered as a fixed dose. In the Dose Escalation part, subjects will be administered GEN1044 according to dose levels outlined in Section 4.2. In the Expansion part, subjects will be administered GEN1044 with the recommended dose from the escalation.

As a routine precaution, subjects dosed with GEN1044 must be monitored during infusion and treated in an area with resuscitation equipment and emergency agents. For weekly dosing during Cycle 1 and Cycle 2, all subjects must be observed for at least 4 hours after ending infusion of GEN1044. For all subsequent cycles, subjects must be observed for at least 2 hours after ending infusion of GEN1044. See Section 4.2 for additional details regarding when an overnight stay (24 hours in-hospital observation) is required.

Refer to the administration and preparation guideline in the GCT1044-01 IMP Manual for additional guidance on trial drug preparation, handling, and storage.

† or equivalent, including oral dose.

Version: 4.0

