3.2 Sample size

Escalation Part

The mBOIN design, as described in Section 4.2.1.1 of the protocol, will enrol up to 58 subjects. Enrolment may be halted based on the pre-specified stopping rules as described in Section 4.2.1 of the protocol.

The initial cohort size is single subject. The cohort size will be expanded to 3 subject cohorts if a DLT or Grade \geq 2 AE within the first 21 days of Cycle 1 is observed in a single subject cohort. (After this, all subsequent cohorts are planned as 3 subject cohorts.) Further details are provided in Section 4.2 of the protocol.

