3.3 Treatment administration schedule

GEN1044 will be infused intravenously in 21-day cycles, as per Section 4.1 of the protocol:

- Cycle 1-4: Day 1, 8, and 15
- Cycles 5 and later: Day 1 only

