7.3 Prior Anti-Cancer Therapy

- The following Prior Anti-cancer therapy will be summarized: the number of prior anti-cancer therapies (One prior line, Two prior lines, Three prior lines, ≥3 prior lines, and Missing)
- Type of prior therapies (Platinum-based therapy, Anti-EGFR therapy, Anti-PD-1/PDL1 therapy, Systemic therapy, Prior Radiotherapy, Prior surgery related to the disease)
- Best response to last prior cancer therapy (as collected in eCRF; CR, PR, SD, PD, NE)

8 Exposure and Compliance

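### Dose intensity per cycle started drifts with time on treatment and misses pure delays; the SAP drops it undeclared and also carries a superseded escalation maximum of 58

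*Protocol*

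**What the plan says.** **Dose intensity.** Protocol 11.4 plans a descriptive summary of dose intensity, "computed as the ratio of actual cumulative dose received and number of cycles initiated". Neither planned dose nor calendar time enters the definition. The same section plans summaries of exposure duration, cumulative dose and dose adjustments with reasons, and a listing of all dosing data.

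**Schedule.** Protocol 6.3 first gives "Cycles 1 through 4: Days 1, 8, and 15 (once weekly for a 21-day cycle") and "Cycles 5 and beyond: Day 1 (every 3 weeks for a 21-day cycle"). Later in the same section it says "GEN1044 will be administered using IV infusion on Days 1, 8, and 15 of each 3-week (21-day) treatment cycle". SAP 3.3 has "Cycles 5 and later: Day 1 only".

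**SAP exposure summaries.** SAP 8.2 covers cycles initiated, treatment duration, number of doses, cumulative dose, and the number and total of full doses. It also tabulates interruptions, reductions and delays with reasons. Dose intensity is not on the list. SAP 2.1, which records changes from the protocol, mentions only that efficacy endpoints will be listed and not summarised.

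**Escalation size.** SAP 3.2 says that the design, with reference to Protocol 4.2.1.1, "will enrol up to 58 subjects". Protocol 4.2.1.1 (version 4.0) reads "Escalation stops if 80 subjects have already been dosed", and Protocol 4.4 also plans about 80.

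**Prior lines.** SAP 7.3 lists "One prior line, Two prior lines, Three prior lines, ≥3 prior lines, and Missing".

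**The concern.** Dose per cycle is interpretable when each cycle is planned to deliver the same amount. Here Cycle 1 holds a priming dose and at least one intermediate dose in most cohorts, Cycles 2 to 4 hold three full doses, and later cycles hold one dose under the schedule bullets. Two fully compliant subjects in one cohort can therefore have quite different values because they stayed on treatment for different times. A cohort mean or median then mixes schedule and discontinuation time with adherence.

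The denominator counts cycles, not weeks. Protocol 7.2.1 lets a dose be postponed by up to 6 weeks, extendable to 12 after consultation. A subject who is postponed but eventually receives every dose looks the same as one treated on time.

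The omission from SAP 8.2 leaves a summary specified in the protocol with no stated status. The figure of 58 misdescribes the design in the document that governs the analysis. The overlapping prior-line rows leave a subject with exactly three lines without a unique place.

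**Working it through.** **1. The protocol's own subject numbers.** From Protocol 4.4: 80 + 320 = 400 treated. With 30% screen failure, 400 / 0.70 = 571, which agrees with the stated figure of about 570. With 58 in place of 80: 58 + 320 = 378, and 378 / 0.70 = 540. Neither matches, so the protocol is internally consistent at 80 only. The gap is 80 − 58 = 22 subjects (22 / 80 = 27.5%).

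**2. Dose intensity at full compliance.** Doses come from the 1/3/30 mg row of SAP Table 1.
- Cycle 1: 1 + 3 + 30 = 34 mg.
- Cycles 2 to 4: 3 × 30 = 90 mg each.
- Cycle 5 onward: 30 mg each (Day 1 only), or 90 mg each if dosing is on Days 1, 8 and 15 of every cycle.

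Ratio after n cycles = cumulative dose / n.

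| Cycles | Cumulative dose, Day 1 only from Cycle 5 (mg) | mg/cycle | mg/cycle if three doses in every cycle |
|---|---|---|---|
| 1 | 34 | 34.0 | 34.0 |
| 2 | 124 | 62.0 | 62.0 |
| 4 | 304 | 76.0 | 76.0 |
| 5 | 334 | 66.8 | 78.8 |
| 8 | 424 | 53.0 | 83.0 |
| 12 | 544 | 45.3 | 85.3 |

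Every row is a subject who missed nothing. The ratio drifts under either schedule statement. In the 1/3/60 mg cohort the Day-1-only values are 64.0 after 1 cycle, 151.0 after 4 and 90.3 after 12.

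**3. Delay with all doses given.** Four cycles deliver 304 mg. By the SAP 5.3 rule (last dose date − first dose date + 7), duration is 84 days (12 weeks) without delay and 126 days (18 weeks) with a 6-week delay. A 12-week delay gives 24 weeks.

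| Delay | mg/cycle | mg/week | Relative to no delay |
|---|---|---|---|
| none | 304/4 = 76.0 | 304/12 = 25.3 | 1.00 |
| 6 weeks | 76.0 | 304/18 = 16.9 | 0.67 |
| 12 weeks | 76.0 | 304/24 = 12.7 | 0.50 |

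**4. What the ratio does detect.** One missed 30 mg dose in four cycles gives (304 − 30) / 4 = 68.5. Stopping after Cycle 2 Day 1 gives (34 + 30) / 2 = 32.0, because a cycle with one dose counts as a whole cycle.

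**5. The proposed measure.** Take actual cumulative dose over the dose the cohort's schedule plans for the elapsed time.
- Four cycles on time: 304 / 304 = 1.00.
- Stopping after Cycle 2 Day 1: 64 / 64 = 1.00.
- One missed 30 mg dose in four cycles: 274 / 304 = 0.90.
- Four cycles with a 6-week delay (18 weeks, six planned cycles): 304 / (304 + 2 × 30) = 0.84 with Day 1 only from Cycle 5, or 304 / (304 + 2 × 90) = 0.63 with three doses in every cycle.

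The last line shows why the schedule statements must agree before the denominator can be programmed.

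**6. Prior lines.** A subject with exactly three lines fits both the third and the fourth category. No row holds zero lines, although the Escalation inclusion criterion admits subjects not eligible for standard therapy.

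**The case against.** The strongest reply is that the operative plan does not produce this ratio. SAP 8.2 omits it, and SAP 2.2 describes an abbreviated report. What SAP 8.2 does plan would show a delay: delays are tabulated with reasons, and in the example above treatment duration would read 126 days instead of 84. Dose per cycle is also a legitimate absolute summary, and the protocol does not call it a measure of compliance. All of this stands and limits the consequence. It does not repair the definition in Protocol 11.4 or explain why SAP 2.1 is silent about dropping the measure.

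Some stronger readings are tempting and are not supported:
- A reader might infer that the ratio cannot show under-dosing. It can: skipped and reduced doses lower it. Only postponement with every dose eventually given is invisible.
- A reader might infer that it ranks subjects by when they stopped. Under the Day-1-only schedule it rises to Cycle 4 and then falls, so it gives no such ordering.
- A reader might infer that the prior-therapy table will exceed 100%. That requires counting one subject in two rows, which nothing specifies. SAP Section 7 leaves category details to the data presentation specification, which is not among the documents. Nor do the documents show that any subject without a prior line was enrolled.
- A reader might infer that the figure of 58 affects an analysis. No denominator or decision in the SAP uses it. SAP 1.2 says enrolment was stopped, and the list of Amendment 3 changes suggests that 58 is a carry-over from version 3.0.

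**Conclusion.** The point holds as a limited one about definitions and consistency. At full compliance the protocol's ratio ranges from 34 to 76 mg/cycle over the first four cycles of the 1/3/30 mg cohort. It then falls to 45.3 by Cycle 12 under the Day-1-only schedule. It is unchanged at 76 by a 6-week delay that cuts weekly delivery by a third. These figures assume SAP Table 1 doses and completed cycles, and in the delay case that no dose is lost. The drift itself does not depend on which schedule statement applies.

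The SAP omits the measure without declaring a change from the protocol. The figure of 58 is a plain contradiction of the section it cites, with little practical effect now. The prior-line overlap is close to clerical. None of this alters the dose-limiting toxicity or adverse event analyses.

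**What to change.** 1. In SAP 8.2, add relative dose intensity: actual cumulative dose divided by the dose planned for the subject's cohort over the elapsed time from first dose to the end of the last dosing interval. The interval lengths can follow SAP 5.3. Alternatively, state in SAP 2.1 that the dose intensity of Protocol 11.4 will not be reported.
2. Reconcile the two schedule statements in Protocol 6.3 with each other and with SAP 3.3, so that the planned dose is unambiguous.
3. In SAP 3.2, replace 58 with 80.
4. In SAP 7.3, use mutually exclusive categories: 0, 1, 2, 3, 4 or more, and missing.

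The cost is a few wording changes and, if the first option under item 1 is taken, one derived variable from dosing data already collected and listed.
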